8.3.2 Direct access to source data and documents

The investigator /institution will allow site trial-related monitoring, audits, IRB / IEC review and regulatory inspections. Direct access must be provided to the CRF and all source documents/data, including progress notes, copies of laboratory and medical test results, which must be available at all times for review by the CRA, auditor and regulatory inspector (e.g. FDA). They may review all CRFs and informed consents. The accuracy of the data will be verified by direct comparison with the source documents described in section 8.3.1. The sponsor will also monitor compliance with the protocol and GCP.

8.3.3 Storage period of records

Trial site(s):

The trial site(s) must retain the source and essential documents (including ISF) according to contract or the local requirements valid at the time of the end of the trial (whatever is longer).

Sponsor:

The sponsor must retain the essential documents according to the sponsor's SOPs.

8.4 EXPEDITED REPORTING OF ADVERSE EVENTS

BI is responsible to fulfil their legal and regulatory reporting obligation in accordance with regulatory requirements.

Exemptions from expedited reporting are described in section 5.2.6.2.4, if applicable.

c27983101-03 Clinical Trial Protocol Page 71 of 79

Proprietary confidential information © 2020 Boehringer Ingelheim International GmbH or one or more of its affiliated companies

8.5 STATEMENT OF CONFIDENTIALITY AND PATIENT PRIVACY

Data protection and data security measures are implemented for the collection, storage and processing of patient data in accordance with the principles 7 and 12 of the WHO GCP handbook.

Individual patient data obtained as a result of this trial is considered confidential and disclosure to third parties is prohibited with the following exceptions:

Personalised treatment data may be given to the patient's personal physician or to other appropriate medical personnel responsible for the patient's welfare. Data generated at the site as a result of the trial need to be available for inspection on request by the participating physicians, the sponsor's representatives, by the IRB / IEC and the regulatory authorities.

8.5.1 Collection, storage and future use of biological samples and corresponding data

Measures are in place to comply with the applicable rules for the collection, biobanking and future use of biological samples and clinical data, in particular

- Sample and data usage has to be in accordance with the separate biobanking informed consent
- The BI-internal facilities storing biological samples from clinical trial participants as well as the external banking facility are qualified for the storage of biological samples collected in clinical trials
- An appropriate sample and data management system, incl. audit trail for clinical data and samples to identify and destroy such samples according to ICF is in place
- A fit for the purpose documentation (biomarker proposal, analysis plan and report) ensures compliant usage
- A fit for purpose approach will be used for assay/equipment validation depending on the intended use of the biomarker data
- Samples and/or data may be transferred to third parties and other countries as specified in the biobanking ICF

8.6 TRIAL MILESTONES

The **start of the trial** is defined as the date when the first subject in the whole trial signs informed consent.

The end of the trial is defined as the date of the last visit of the last subject in the whole trial ("Last Patient Completed"). The "Last Patient Last Treatment" (LPLT) date is defined as the date on which the last patient in the whole trial is administered the last dose of trial treatment (as scheduled per protocol or prematurely). Individual investigators will be notified of SUSARs occurring with the trial medication until 30 days after LPLT at their site.

c27983101-03 Clinical Trial Protocol Page 72 of 79

Proprietary confidential information © 2020 Boehringer Ingelheim International GmbH or one or more of its affiliated companies

Early termination of the trial is defined as the premature termination of the trial due to any reason before the end of the trial as specified in this protocol.

Temporary halt of the trial is defined as any unplanned interruption of the trial by the sponsor with the intention to resume it.

Suspension of the trial is defined as an interruption of the trial based on a Health Authority request.

A final report of the clinical trial data will be written only after all subjects have completed the trial to incorporate and consider all data in the report.

8.7 ADMINISTRATIVE STRUCTURE OF THE TRIAL

The trial is sponsored by Boehringer Ingelheim (BI).

The trial will be conducted at one clinical site. A Principal Investigator is responsible to coordinate co-investigators at the site participating in this trial. Tasks and responsibilities are defined in a contract.

Relevant documentation on the participating Investigators (e.g. their curricula vitae) will be filed in the ISF.

BI has appointed a Clinical Trial Leader (CT Leader), responsible for coordinating all required activities, in order to

- manage the trial in accordance with applicable regulations and SOPs applicable in a FOT setting,
- direct the clinical trial team in the preparation, conduct, and reporting of the trial,
- ensure appropriate training and oversight of the vendors.

The organisation of the trial will be performed by a Contract Research Organisation (CRO) with which the responsibilities and tasks will have been agreed and a written contract filed before initiation of the clinical trial.

CRO will perform Project Management, Clinical Field Monitoring, Medical Monitoring, Data Management, Statistical Evaluation and Reporting.

Tasks and functions assigned in order to organise, manage, and evaluate the trial are defined according to BI and CRO SOPs. A list of responsible persons and relevant local information can be found in the ISF.

c27983101-03 Clinical Trial Protocol Page 73 of 79

Proprietary confidential information © 2020 Boehringer Ingelheim International GmbH or one or more of its affiliated companies

10. APPENDICES

10.1 RESTRICTED MEDICATION AND FOOD

Other investigational products	• 30 days or 5 half-lives, whatever is longer, prior to randomization through EOT
Disease, surgery	Major surgery performed within 8 weeks prior to screening visit or planned within 8 weeks after screening visit (e.g. hip replacement)
-Drugs or foods (e.g., seville oranges, grapefruit, paw paw and their products) which are strong or moderate inhibitors or inducers of CYP3A4 (e.g, rifampicin, phenytoin), or -Sensitive substrates of CYP1A2 (e.g., alosetron, duloxetine, melatonin, ramelteon, tasimelteon, theophylline, tizanidine, and caffeine when used as a medication), or -Sensitive substrates of CYP 2B6 (e.g., bupropion).	 One week prior to randomisation until EOT (Sensitive substrates of CYP3A4 are not excluded from the trial).
Drugs which are substrates of P-gp (e.g. dabigatran, digoxin and fexofenadine etc.)	One week prior to randomisation until EOT
Drugs with known phototoxic or photoallergic potential (e.g., tetracyclines, fluoroquinolones)	One week prior to randomisation until EOT
BCG (Bacillus Calmette-Guérin) vaccine	1 year prior to randomisation through 1 year after last administration of study drug

c27983101-03 Clinical Trial Protocol Page 75 of 79

Proprietary confidential information © 2020 Boehringer Ingelheim International GmbH or one or more of its affiliated companies

10.2 TIME SCHEDULE FOR PHARMACOKINETIC (PK) BLOOD SAMPLING

Table 10.2: 1 Time schedule for PK blood sampling during treatment course A 400 mg QD

Day	Time Point [hh:min] ¹	CRF Time /PTM	Event	Sample No.
1	Just before drug administration	-1:00	PK Blood	1
	0:00	0:00	1 st Drug administr.	
	4:00	4:00	PK Blood	2
2	8:00/Predose	24:00	PK Blood	3
3	8:00/Predose	48:00	PK Blood	4
4	8:00/Predose	72:00	PK Blood	5
5	8:00/Predose	96:00	PK Blood	6
6	8:00/Predose	120:00	PK Blood	7
7	8:00/Predose	144:00	PK Blood	8
8	8:00/Predose	168:00	PK Blood	9
	9:00	169:00	PK Blood	10
	10:00	170:00	PK Blood	11
	11:00	171:00	PK Blood	12
	12:00	172:00	PK Blood.	13
	14:00	174:00	PK Blood	14
	20:00	180:00	PK Blood	15
9	8:00	192:00	PK Blood	16
10	8:00	216:00	PK Blood	17
11	8:00	240:00	PK Blood	18

Time windows allowed for PK sampling:

Within 1 h pre-dose and 4 h post dose on day 1; -10 min pre-dose samples on days 2 to 8; +/- 5 min 1/2/3/4/6/12 h on day 8; +/- 15 min on days 9/10/11.

c27983101-03 Clinical Trial Protocol Page 76 of 79

Proprietary confidential information © 2020 Boehringer Ingelheim International GmbH or one or more of its affiliated companies

Table 10.2: 2 Time schedule for PK blood sampling during treatment course A 300 mg BID

Day	Time Point [hh:min] ^{1,2}	CRF Time /PTM	Event	Sample No.
1	Just before drug administration	-1:00	PK Blood	1
	8:00	0:00	1 st Drug administr.	
	9:00	1:00	PK Blood	2
	10:00	2:00	PK Blood	3
	11:00	3:00	PK Blood	4
	12:00	4:00	PK Blood	5
	14:00	6:00	PK Blood	6
	16:00	8:00	PK Blood	7
	18:00	10:00	PK Blood	8
	20:00	12:00	PK Blood	9
5	8:00/Predose	96:00	PK Blood	10
6	8:00/Predose	120:00	PK Blood	11
7	8:00/Predose	144:00	PK Blood	12
8	8:00/Predose	168:00	PK Blood	13
	9:00	169:00	PK Blood	14
	10:00	170:00	PK Blood	15
	11:00	171:00	PK Blood	16
	12:00	172:00	PK Blood.	17
	14:00	174:00	PK Blood	18
	20:00	180:00	PK Blood	19
9	8:00	192:00	PK Blood	20
10	8:00	216:00	PK Blood	21
11	8:00	240:00	PK Blood	22

¹ Time windows allowed for PK sampling:

Within 1 h pre-dose and 4 h post dose on day 1; -10 min pre-dose samples on days 5 to 8; \pm 5 min \pm 1/2/3/4/12 h on day 8; \pm 15 min on days 9/10/11.

² All timepoints are relative to the drug administration time.

c27983101-03 Clinical Trial Protocol Page 77 of 79

Proprietary confidential information © 2020 Boehringer Ingelheim International GmbH or one or more of its affiliated companies

11. DESCRIPTION OF GLOBAL AMENDMENT(S)

11.1 GLOBAL AMENDMENT 1

Date of amendment	05 Mar 2020		
BI Trial number	1407-0037		
BI Investigational Medicinal Product	BI 730357		
Title of protocol	Partially-blind, randomized, parallel group, placebo and active comparator-controlled Phase I clinical trial to evaluate the photosensitivity potential of BI 730357		
To be implemented only after approval of the IRB / IEC / Competent Authorities			
-	ly in order to eliminate hazard – IRB / IEC / tified of change with request for approval		
Can be implemented without IRB / IEC / Competent Authority approval as changes involve logistical or administrative aspects only			
Section to be changed	4.1.5.1 Blinding;		
section to be changed	7.2.7 Interim analysis;		
Description of change	The following sentence was added on page 38:		
	In addition, the trial pharmacokineticist may receive the blinded (dummy subject numbers will be used) results of the measurements to perform the preliminary PK analysis.		
	The following sentence was added on page 62:		
	In addition, a preliminary blinded PK analysis will be performed to estimate the PK exposure.		
Rationale for change	The administrative amendment is incorporated to allow preliminary analysis of blinded PK data. The results from the blinded PK analysis will be compared with the historical data upon which the study was designed. This blinded evaluation possibility was overseen in the original protocol, and is now added per this non-substantial amendment		

c27983101-03 Clinical Trial Protocol Page 78 of 79

Proprietary confidential information © 2020 Boehringer Ingelheim International GmbH or one or more of its affiliated companies

[figure not shown]
11.2 GLOBAL AMENDMENT 2

Date of amendment	01 Apr 2020		
BI Trial number	1407-0037		
BI Investigational Medicinal Product	BI 730357		
Title of protocol	Partially-blind, randomized, parallel group, placebo and active comparator-controlled Phase I clinical trial to evaluate the photosensitivity potential of BI 730357		
To be implemented only after Authorities	approval of the IRB / IEC / Competent		
I	ely in order to eliminate hazard – IRB / IEC / tified of change with request for approval		
Can be implemented without l changes involve logistical or ac	IRB / IEC / Competent Authority approval as dministrative aspects only		
Section to be changed	Synopsis; Flow chart 300 mg BID; 1.4.2 Risks;		
	1.4.2 RISKS; 3.1 Overall Trial Design; 3.2 Discussion of Trial Design; 4.1.1 Investigational Treatments;		
	4.1.2 Selection of doses in the trial and dose modifications		
	7.5 Determination of Sample size analysis;		
Description of change	Additional dose group 300 mg of BI 730357 or Placebo BID has been added.		
Rationale for change	Results of the Week 12 primary analysis for trial 1407-0030 demonstrated proof-of-concept, as well as acceptable safety and tolerability in the treatment of patients with moderate-to-severe plaque PsO for BI 730357 at the 200 mg dose;		
	Modelling of primary analysis data indicates that the efficacy plateau of BI 730357 may not have been reached with 200 mg dose q.d., and that higher exposures may provide better efficacy. Therefore efficacy, safety, tolerability, and pharmacokinetics of BI 730357 400 mg q.d. and 200 mg b.i.d. will be		

c27983101-03 Clinical Trial Protocol Page 79 of 79

Proprietary confidential information © 2020 Boehringer Ingelheim International GmbH or one or more of its affiliated companies

evaluated as possible therapeutic doses in patients.
Psoriasis patients have shown higher exposures than those of healthy volunteers; therefore in order to investigate possible phototoxic effects in exposures which approximate those of patients treated with 200 mg b.i.d., healthy volunteers will be treated with 300 mg b.i.d. under fed conditions in this trial.

APPROVAL / SIGNATURE PAGE

Document Number: c27983101 Technical Version Number: 3.0

Document Name: clinical-trial-protocol-version-03

Title: Partially-blind, randomized, parallel group, placebo and active comparator-controlled Phase I clinical trial to evaluate the photosensitivity potential of BI 730357

Signatures (obtained electronically)

Meaning of Signature	Signed by	Date Signed
Author-Clinical Trial Leader		01 Apr 2020 14:53 CEST
Author-Trial Statistician		01 Apr 2020 15:02 CEST
Author-Trial Clinical Pharmacokineticist		01 Apr 2020 16:00 CEST
Approval-Therapeutic Area		01 Apr 2020 16:19 CEST
Approval-Team Member Medicine		01 Apr 2020 18:37 CEST
Verification-Paper Signature Completion		01 Apr 2020 18:38 CEST

Boehringer IngelheimPage 2 of 2Document Number: c27983101Technical Version Number: 3.0

(Continued) Signatures (obtained electronically)

Meaning of Signature	Signed by	Date Signed
----------------------	-----------	-------------

1. INTRODUCTION

As per ICH E9, the purpose of this document is to provide a more technical and detailed elaboration of the principal features of the analysis described in the protocol, and to include detailed procedures for executing the statistical analysis of the primary and secondary variables and other data. This trial statistical analysis plan (TSAP) assumes familiarity with the Clinical Trial Protocol (CTP), including Protocol Amendments. In particular, the TSAP is based on the planned analysis specification as written in CTP Section 7 "Statistical Methods and Determination of Sample Size". Therefore, TSAP readers may consult the CTP for more background information on the study, e.g., on study objectives, study design and population, treatments, definition of measurements and variables, planning of sample size, randomization

This TSAP Version 2.0 is based on Protocol Version 3.0, (ie, Amendment 2) dated 01 April 2020 and is an amendment to the TSAP Version 1.0 which was finalized on 26 February 2020. This TSAP amendment adds a description of the statistical analysis of the additional dose group of 300 mg BID (subjects randomized to BI 730357 300 mg BID or placebo 300 mg BID) added to the study by the above mentioned protocol.

For the assessment of photosensitivity, statistical analyses for both the double-blind randomized 400 mg QD dose group (subjects randomized to BI 730357 400 mg QD or placebo) and the double-blind randomized 300 mg BID dose group (randomized to BI 730357 300 mg BID or placebo) will be identical but will be performed separately.

This TSAP is developed using the [REDACTED] statistical analysis plan templates. The operating procedures (SOPs) and programming standards of the Sponsor will be followed for this study.

2. STUDY OBJECTIVES

2.1. PRIMARY OBJECTIVE

The primary objective of this trial is to evaluate the photosensitivity potential of BI 730357 compared to placebo and a mild photosensitizer ciprofloxacin as positive control, assessed by the Photosensitivity Index (PI), changes in Minimum Erythema Dose (MED), erythema, and local skin reactions following exposure to UVA and UVB radiation. All endpoints are applicable for Treatment A and Treatment B parts.

Document: L:\BIOS\Boehringer_Ingelheim_Pharmaceuticals\BI730357\1407-0037_MZA56588\Biostatistics\Documentation\SAP

Author: [REDACTED] Version Number: Final V2.0
Version Date: 23JUL2020

Template No: CS_TP_BS016 – Revision 5
Effective Date: 01Apr2018

[figure not shown]
Reference: CS_WI_BS005

2.1.1. PRIMARY ENDPOINTS

- Photosensitivity index at 24 hours under Condition 1 (i.e., under full range of UVB/UVA exposure)
- Photosensitivity index at 24 hours under Condition 2 (i.e., under UVA exposure only)

2.1.2. SECONDARY ENDPOINTS

- Photosensitivity index at 10 minutes under Condition 1
- Photosensitivity index at 1 hour under Condition 1
- Photosensitivity index at 10 minutes under Condition 2
- Photosensitivity index at 1 hour under Condition 2
- MED percent change from baseline at 10 minutes, 1 hour, and 24 hours measured under Condition 1 and Condition 2

[figure not shown]

Document: L:\BIOS\Boehringer_Ingelheim_Pharmaceuticals\BI730357\1407-0037_MZA56588\Biostatistics\Documentation\SAP

Author: [REDACTED] Version Number: Final V2.0
Version Date: 23JUL2020

Template No: CS_TP_BS016 – Revision 5
Effective Date: 01Apr2018

Reference: CS_WI_BS005

2.3. SAFETY OBJECTIVES

Safety and tolerability objectives are to be assessed in terms of adverse events (AEs), including AEs of special interest (AESIs), laboratory assessments, vital signs, electrocardiograms (ECG), and physical examination.

3. STUDY DESIGN

3.1. GENERAL DESCRIPTION

The trial will be performed as partially-blind, randomized, parallel group, placebo and active comparator controlled Phase I clinical trial in healthy male and female subjects aged ≥ 18 to ≤ 55 years. The subjects

Document: L:\BIOS\Boehringer_Ingelheim_Pharmaceuticals\BI730357\1407-0037_MZA56588\Biostatistics\Documentation\SAP

Author: [REDACTED] Version Number: Final V2.0
Version Date: 23JUL2020

Template No: CS_TP_BS016 – Revision 5
Effective Date: 01Apr2018

Reference: CS_WI_BS005

will be randomized to one of the two treatments parts (Treatment Part A [Treatment A] or Treatment Part B [Treatment B]) in a 3:1 (A:B) manner first and then Treatment Part A will be conducted according to a randomized, double-blind, placebo-controlled design to assess the photosensitivity potential, safety and tolerability, and pharmacokinetics of multiple doses of BI 730357. In Treatment A, subjects enrolled under the original protocol Version 1.0 will be randomized in a 3:1 manner to receive 400 mg QD of BI 730357 or placebo and subjects enrolled under the protocol Version 3.0 will be randomized in a 3:1 manner to receive 300 mg BID of BI 730357 or placebo.

Treatment Part B will be conducted according to an open-label, observer-blinded design to assess the photosensitivity potential of ciprofloxacin (a mild photosensitizer) as a positive control.

In total, approximately 84 healthy male and female subjects (36 subjects in Treatment A for 400 mg QD; 36 subjects in Treatment A for 300 mg BID; 12 subjects in Treatment B) are planned to be randomized in this trial to allow for at least 74 completed subjects.

Treatment A:

Subjects enrolled under Protocol Version 1.0 will receive 400 mg of BI 730357 or placebo once daily over 8 days in order to reach pharmacokinetic steady state. Similarly, subjects enrolled under Protocol Version 3.0 will receive 300 mg of BI 730357 or placebo twice daily 12 hours apart over 7 days with a single dose on Day 8 in order to reach pharmacokinetic steady state. Photosensitivity assessments will occur at baseline and following the last dose of either BI 730357 or placebo.

Treatment B:

Subjects will receive 500 mg ciprofloxacin starting on the morning of Day 3. Twelve (12) hours later, subjects received their second dose of 500 mg ciprofloxacin. Subjects continued a twice-daily dosing regimen through to the morning of Day 8 to ensure they reached pharmacokinetic steady state. Photosensitivity assessments will occur at baseline and following the last dose of ciprofloxacin.

3.2. SCHEDULE OF EVENTS

Visit schedules can be found in the protocol (see Flow Chart for Treatment A and Flow Chart for Treatment B).

3.3. CHANGES TO ANALYSIS FROM PROTOCOL

The further objective of [REDACTED] will not be performed for this study.

The primary, secondary [REDACTED] endpoints referred in the protocol as "Phototoxicity index" are changed to the appropriate name "Photosensitivity index" (see Sections 2.1.1, 2.1.2 and 2.2.1 above).

Document: L:\BIOS\Boehringer_Ingelheim_Pharmaceuticals\BI730357\1407-0037_MZA56588\Biostatistics\Documentation\SAP

Author: [REDACTED] Version Number: Final V2.0
Version Date: 23JUL2020

Template No: CS_TP_BS016 – Revision 5
Effective Date: 01Apr2018

Reference: CS_WI_BS005

4. PLANNED ANALYSES

4.1. INTERIM ANALYSIS

There are no formal statistical interim analyses planned for this study. However, after completion of the 400mg dose group, the independent Investigator and BI medical representatives will review blinded photosafety data of treatment A group to determine the acceptability of photosafety. After the team review of these data, it may be recommended to terminate the trial based on favourable results of 400mg, or in case of unfavourable results - to test the lower dose in of 200mg for treatment A. However, primary analysis of ongoing PoC trial have shown higher exposures in Psoriasis patients than those of healthy volunteers; therefore, in order to investigate possible phototoxic effects in exposures which approximate those of patients treated with 200 mg BID, healthy volunteers should be treated with 300 mg BID. under fed conditions in this trial.

4.2. FINAL ANALYSIS

All final, planned analyses identified for non-PK data in this SAP will be performed by [REDACTED] Biostatistics following sponsor authorization of this Statistical Analysis Plan, identification of important protocol deviations requiring analysis exclusions, database lock, determination of analysis sets, and unblinding of treatment. All final, planned analyses for PK data will be performed by the Sponsor.

5. ANALYSIS SETS

Agreement and authorization of subjects included/ excluded from each analysis set will be conducted prior to the unblinding of the study.

5.1. ENROLLED SET (ES)

The enrolled set will contain all subjects who provide informed consent for this study. Subjects in this population will be used for disposition summaries and listings as appropriate.

5.2. TREATED SET (TS)

The treated set includes all subjects who were randomized and treated with at least one dose of study drug (BI 730357, Placebo or ciprofloxacin). The treated set will be used for safety analyses and randomized treatment will be used for safety analysis.

Document:	L:\BIOS\Boehringer_Ingelheim_Pharmaceuticals\BI730357\1407-0037_MZA56588\Biostatistics\Documentation\SAP		
Author:	[REDACTED]	Version Number:	Final V2.0
		Version Date:	23JUL2020
Template No:	CS_TP_BS016 – Revision 5		
Effective Date:	01Apr2018		
Copyright © 2009, 2010, 2012, 2016, 2018 [REDACTED] All Rights Reserved. The contents of this document are confidential and proprietary to [REDACTED] and its subsidiaries. Unauthorized use, disclosure or reproduction is strictly prohibited.		Reference: CS_WI_BS005	

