7.2 PLANNED ANALYSES

7.2.1 General considerations

Analysis sets

Statistical analyses will be based on the following analysis sets:

- Treated set (TS): The treated set includes all subjects who were randomized and treated with at least one dose of study drug. The treated set will be used for safety analyses.
- Full analysis set (FAS): This set includes all subjects in the treated set (TS) who provide at least one photosensitivity endpoint that was defined as primary or secondary and was not excluded due to a protocol deviation relevant to the evaluation

c27983101-03 Clinical Trial Protocol Page 64 of 79

Proprietary confidential information © 2020 Boehringer Ingelheim International GmbH or one or more of its affiliated companies

of photosensitivity. Descriptive and model based analyses of photosensitivity endpoints will be based on the FAS.

Additional analysis sets, refinements of the above definitions, or other relevant details may be specified in the TSAP. The implications that patients with important protocol deviations (including receiving incorrect medication) might have on the analysis will be discussed at the report planning meeting(s) and decisions will be documented in the decision log.

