7.2.5 Safety analyses

Adverse events will be coded using the Medical Dictionary for Drug Regulatory Activities (MedDRA). Standard BI summary tables and listings will be produced. All adverse events with an onset between start of treatment and end of the REP, a period of 7 days after the last dose of trial medication, will be assigned to the on-treatment period for evaluation.

The safety analysis will be done by 'randomised treatment'.

All treated subjects will be included in the safety analysis. In general, safety analyses will be descriptive in nature and will be based on BI standards. No hypothesis testing is planned.

Statistical analysis and reporting of adverse events will concentrate on treatment-emergent adverse events, i.e. all adverse events occurring between start of treatment and end of the REP. Adverse events that start before first drug intake and deteriorate under treatment will also be considered as 'treatment-emergent'.

Frequency, severity, and causal relationship of adverse events will be tabulated by system organ class and preferred term after coding according to the current version of the Medical Dictionary for Drug Regulatory Activities (MedDRA) at database lock.

c27983101-03 Clinical Trial Protocol Page 66 of 79

Proprietary confidential information © 2020 Boehringer Ingelheim International GmbH or one or more of its affiliated companies

Laboratory data will be analysed both quantitatively as well as qualitatively. The latter will be done via comparison of laboratory data to their reference ranges. Values outside the reference range as well as values defined as clinically relevant will be summarised. Treatment groups will be compared descriptively with regard to distribution parameters as well as with regard to frequency and percentage of subjects with abnormal values or clinically relevant abnormal values.

Vital signs, physical examinations, or other safety-relevant data observed at screening, baseline, during the course of the trial and at the end-of-trial evaluation will be assessed with regard to possible changes compared to findings before start of treatment.

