11. PROTOCOL DEVIATIONS

11.1. DEVIATIONS RELATED TO STUDY CONDUCT

A protocol deviation is any noncompliance with the clinical trial protocol, good clinical practice (GCP), or Manual of Procedure requirements. The noncompliance may be either on the part of the subject, the site principal investigator, or the study site staff. Protocol deviations will be listed including a

Document: L:\BIOS\Boehringer_Ingelheim_Pharmaceuticals\BI730357\1407-0037_MZA56588\Biostatistics\Documentation\SAP

Author: [REDACTED] Version Number: Final V2.0
Version Date: 23JUL2020

Template No: CS_TP_BS016 – Revision 5
Effective Date: 01Apr2018

Reference: CS_WI_BS005

classification of minor, major or critical as determined by clinical staff. Whether a protocol deviation is relevant for the statistical analysis will be decided no later than in the final blinded report planning meeting.

The reasons for exclusion of single data may include (but are not limited to):

- Incorrect trial medication taken
- Important violation of treatment compliance
- Use of restricted medications
- Important violation of inclusion/exclusion criteria
 - Inclusion Criteria 1 - Healthy male and female subjects according to the assessment of the Investigator, based on a complete medical history, physical examination (including dermatological skin type assessment), vital signs (blood pressure, pulse rate), 12-lead ECG, and clinical laboratory tests
 - Inclusion Criteria 4 - Fitzpatrick skin type I, II, or III (I: always burns easily, never tans; II: always burns easily, tans minimally; and III: burns moderately, tans gradually)
 - Inclusion Criteria 5 - No ultraviolet exposure of the test areas 4 weeks prior to baseline photo testing
 - Inclusion Criteria 6 - Normal skin response during preliminary photo testing
 - Exclusion Criteria 6 - Active skin disorders on the back where photosensitivity testing will be performed
 - Exclusion Criteria 7 - Subjects who must or wish to continue the intake of restricted medications or any drug considered likely to interfere with the safe conduct of the trial
 - Exclusion Criteria 12 - -History of hypersensitivity to ciprofloxacin, any member of the quinolone class of antibacterials
 - Exclusion Criteria 22 - -Unwillingness to adhere to the rules of UV-light protection as described in section 4.2.2 of the protocol

Document: L:\BIOS\Boehringer_Ingelheim_Pharmaceuticals\BI730357\1407-0037_MZA56588\Biostatistics\Documentation\SAP

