17. SAFETY OUTCOMES

All safety assessments, including AEs, clinical laboratory evaluations, and vital signs will be listed and where appropriate summarized with descriptive statistics by treatment and scheduled visit/time point. Safety summaries will be provided for the following treatment group: Placebo Pooled (pooled from 2 dose groups), BI 730357 400 mg QD, BI 730357 300 mg BID, BI 730357 Pooled (pooled from 2 dose groups) and Ciprofloxacin 500 mg BID. All summaries for safety outcomes will be based on the treated set using the randomized treatment.

No statistical hypothesis testing is planned for safety data, unless otherwise specified with the relevant section.

Document: L:\BIOS\Boehringer_Ingelheim_Pharmaceuticals\BI730357\1407-0037_MZA56588\Biostatistics\Documentation\SAP

Author: [REDACTED] Version Number: Final V2.0
Version Date: 23JUL2020

Template No: CS_TP_BS016 – Revision 5
Effective Date: 01Apr2018

Reference: CS_WI_BS005

Copyright © 2009, 2010, 2012, 2016, 2018 [REDACTED] All Rights Reserved. The contents of this document are confidential and proprietary to [REDACTED] and its subsidiaries. Unauthorized use, disclosure or reproduction is strictly prohibited.

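### Safety is tabulated by randomised treatment with no rule for a mis-dosed subject, so if mis-dosing occurs that subject's events would by default be counted under a drug not taken

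*SAP*

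**What the plan says.** Three places fix how safety data are assigned to a treatment column. SAP 5.2 (Treated Set) says "The treated set will be used for safety analyses and randomized treatment will be used for safety analysis". SAP 17 (Safety Outcomes) repeats it: "All summaries for safety outcomes will be based on the treated set using the randomized treatment". Protocol 7.2.5 has "The safety analysis will be done by", and the sentence ends with randomised treatment. None of the three carries an exception.

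Both documents also foresee that a subject may be given the wrong product. Protocol 7.2.1 speaks of "patients with important protocol deviations (including receiving incorrect medication" and sends the implications for the analysis to the report planning meeting, with the outcome logged. SAP 11.1 puts "Incorrect trial medication taken" first among its reasons for leaving out single data, and sets the timing: "Whether a protocol deviation is relevant for the statistical analysis will be decided no later than in the final blinded report planning meeting".

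The full analysis set (SAP 5.3) and the pharmacokinetic set (SAP 5.4) can each drop a subject for an important deviation that matters to their purpose. The treated set cannot. It asks only for randomisation and one dose of study drug.

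**The concern.** A safety table is read as an account of what happened to people who took each product. Where received and randomised treatment differ, the written rule gives a different account: the subject's adverse events and laboratory values stay in the column of the product not taken. The plan names the circumstance and provides for it in the photosensitivity and pharmacokinetic sets, but leaves the safety default unchanged.

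The direction depends on the error. If a placebo-randomised subject receives BI 730357 and has a drug-related event, the event raises the placebo rate and is missing from the active rate. That makes the drug look more like placebo, which is the less cautious direction for safety. If a subject randomised to BI 730357 receives placebo, a background event is charged to the drug.

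The groups are small, so a single subject shows in the percentages.

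**Working it through.** The plan states no figure on this point, so there is none to reproduce. The check compares the texts and then sizes the effect of one subject.

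**Inputs**
- Planned group sizes: 27 active and 9 placebo in each Part A dose cohort, and 12 on ciprofloxacin (Protocol 3.2).
- Safety columns (SAP 17): pooled placebo, BI 730357 400 mg QD, BI 730357 300 mg BID, pooled BI 730357, ciprofloxacin.
- Column sizes: pooled placebo 9 + 9 = 18; each BI 730357 dose group 27; pooled BI 730357 27 + 27 = 54; ciprofloxacin 12.
- Cut-off for the table of common non-serious treatment-emergent events: above 5% in at least one group (SAP 17.1).

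**Step 1: weight of one subject.** The formula is 100 × 1/n. The number of subjects needed to exceed 5% is the smallest k with k/n > 0.05.

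| Safety column | n | One event | Subjects needed to exceed 5% |
|---|---|---|---|
| Placebo pooled | 18 | 1/18 = 5.6% | 1 |
| Ciprofloxacin | 12 | 1/12 = 8.3% | 1 |
| BI 730357, either dose | 27 | 1/27 = 3.7% | 2 (2/27 = 7.4%) |
| BI 730357 pooled | 54 | 1/54 = 1.9% | 3 (3/54 = 5.6%) |

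One misplaced event is therefore enough to carry a preferred term over the cut-off in the pooled placebo or ciprofloxacin column.

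**Step 2: worked cases.** Each assumes one subject on the wrong product throughout, one event, and no other subject with that event.

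- Randomised to placebo, received BI 730357 400 mg QD.
  - As written: placebo 1/18 = 5.6%, BI 400 mg 0/27 = 0%.
  - By treatment received: placebo 0/17 = 0%, BI 400 mg 1/28 = 3.6%.
  - The sign of the difference reverses. The common-event table also changes: as written, the term qualifies because of placebo; by treatment received, 3.6% is below the cut-off and the term appears only in the full event tables.
- Randomised to BI 730357 400 mg QD, received placebo.
  - As written: BI 400 mg 1/27 = 3.7%, placebo 0/18 = 0%.
  - By treatment received: BI 400 mg 0/26 = 0%, placebo 1/19 = 5.3%.

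**Step 3: what the effect reaches.** Under SAP 15.2 the photosensitivity endpoints are analysed in the full analysis set, and SAP 15.4 draws the photosafety conclusion from the confidence interval for PI. Incorrect medication can lead to exclusion there. SAP 17 and Protocol 7.2.5 plan no safety hypothesis tests. What remains is the descriptive adverse event and laboratory tables.

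**The case against.** The best defence has five parts.

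1. *There is no contradiction.* The protocol and the SAP agree in three places, so this is a stated convention and not an error. That is correct. The point is that another convention describes safety better in the one case where the two differ.
2. *Mis-dosing is unlikely.* Protocol 4.3 has all doses given on site under supervision, with plasma concentrations as further confirmation. The first part stands, and the documents give no mis-dosing rate. The second gives less reassurance for the placebo case, because Protocol 4.1.5.1 allows samples from placebo subjects to be left out of the bioanalysis.
3. *There is a process.* Protocol 7.2.1 lets the report planning meeting consider incorrect medication and does not confine this to photosensitivity. A correction is therefore possible, and it would be wrong to say that events will inevitably be misplaced. But the outcome is not pre-specified, and if the meeting decides nothing the randomised rule applies.
4. *The facts will be visible.* SAP 9, 11.1 and 14 provide listings of randomisation, drug administration and deviations, so a careful reader could reassign an event by hand. That does not correct the summary tables, and Appendix 1 orders listings by randomised group.
5. *Received treatment is not self-defining.* The regimens run to 8, 15 or 11 doses (SAP 14). Moving a subject wholesale after one wrong dose could itself misplace events. This stands, and the fix has to deal with it.

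Two stronger readings are tempting, and the documents do not support them. A reader might take the 9-subject placebo group and claim a shift of 1/9 = 11.1 points, but SAP 17 shows placebo pooled in the safety summaries, so 1/18 is the placebo figure. A reader might also infer that the photosafety conclusion is biased. It is not drawn from the adverse event tables, as step 3 of the working shows.

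**Conclusion.** The point holds as a minor, conditional weakness. If a subject receives the wrong product, and the report planning meeting does not decide otherwise, the written rule counts that subject's adverse events and laboratory values under a drug not taken. One event is worth 5.6 points in pooled placebo, 8.3 in ciprofloxacin and 3.7 in a BI 730357 dose group. In the first worked case this is enough to reverse the apparent direction of a comparison.

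These sizes assume the planned numbers, with every randomised subject treated and none replaced. The worked cases also assume the wrong product throughout and no other subject with the event. If no mis-dosing occurs, both conventions give identical tables. No hypothesis test or photosafety criterion depends on the choice.

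**What to change.** - In SAP 5.2 and 17 and Protocol 7.2.5, tabulate the treated set by treatment actually received. A subject given the wrong product throughout goes under that product.
- Pre-specify the classification for mixed exposure. One workable rule: a placebo-randomised subject who received any dose of BI 730357 counts as BI 730357 for events with onset from that dose; otherwise a subject with mixed exposure stays in the randomised group. State which denominator the subject enters.
- Flag in a listing every subject whose received and randomised treatments differ, showing both.

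The cost is wording in three sections, one derived variable and the mixed-exposure rule, which should be settled before unblinding. The PI analysis and the conduct of the trial do not change, nor do the safety results if every subject received the assigned product.
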